### 3. ANALYSIS POPULATIONS

The primary and secondary endpoints analyses will be conducted based on pre-defined populations as described below.

The primary endpoint per-protocol analysis population will be used to conduct the primary endpoints 1 and 2 analyses because these endpoints are based on SAEFR and SAE rates at 5 years post-implant respectively. The secondary endpoint per-protocol analysis population will be used to conduct the secondary endpoints 5 and 6 analyses because these endpoints examine primary endpoints 1 and 2 based on originally implanted lead models; therefore, are examined at 5 years post-implant. The intention-to-treat population will be used to conduct the secondary endpoints 1 through 4 analyses and all additional data of interest because these endpoints are continuous and examine measurements and event rates throughout the study; therefore, are not limited to only examining subjects who complete 5 year follow-up.

#### 3.1 INTENTION-TO-TREAT (ITT) ANALYSIS POPULATION

The intention-to-treat (ITT) population includes all subjects enrolled in the study. The ITT subjects have documentation of informed consented and implant of the Corox LV study lead. This population includes all subjects enrolled in the study.

#### 3.2 PRIMARY ENDPOINT PER-PROTOCOL (PP) ANALYSIS POPULATION

The primary endpoint per-protocol (PP) population is a subset of the ITT population. The primary endpoint PP subjects have experienced a protocol defined primary endpoint AE or have a follow-up visit or system revision date completed 5 years post-implant (defined as a visit completed on or after 45 days prior to the 5 year post-implant date, 1781 days).

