For the sample size calculation, a maximum loss to follow-up of 10% per year (50% over 5 years) was assumed. The loss to follow-up rate encompasses all causes for subjects to be exited from the study, including subject death, device explants, patient directed withdrawals, physician directed withdrawals, and loss of contact with the subject. BIOTRONIK will make every effort to limit the loss to follow-up, for reasons other than subject death and device explants unrelated to device design or performance, to less than 20% of the total registry enrollment cohort.

Minimum cohort size

The pre-specified secondary analysis will be conducted as an ad hoc analysis, meaning no testable hypothesis is being stated. Therefore, the minimal cohort size to analyze each lead model is based on an assumption of an equal 1/3 distribution of each lead model being enrolled in the CELESTIAL Registry. For the evaluation of the Corox OTW-L BP lead, a minimum of 600 evaluable subjects will be necessary.

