2.7.1 Trend Analyses

The primary safety endpoints are evaluated at 5 years post-enrollment against pre-specified performance levels (92.5% for overall freedom from Corox BP LV lead-rated SAEs, 1% for individual SAE rates). To monitor the ongoing incidence of any potential SAEs against the accumulating follow-up exposure post-enrollment, Kaplan-Meier actuarial survivor curves will be prepared at the reporting intervals for these safety outcomes. Root causes for any failures, regardless of the incidence rates, will be investigated.

If the observed cumulative survival rates fall below the 5-year target values (92.5% for overall freedom from SAEs, 99% for individual SAEs) at any time during the study, or are projected to fall below the target values, then BIOTRONIK will summarize the observed data and the results of its failure investigations, and report the findings to the FDA at or before the next scheduled status report. If at any time a single unanticipated serious adverse event or device failure, or combination of events, is believed to have implications regarding the safety of current or future patients, then this will be reported immediately to the FDA.

CELESTIAL REGISTRY PROTOCOL

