## 1.1 SAMPLE SIZE AND POWER

The estimated sample size requirement is based on both primary safety endpoints: a noninferiority comparison of the overall serious adverse event (SAE) free-rate to 92.5% at 5 years, excluding those SAEs listed in Protocol Table 4, and a non-powered, superiority comparison for those individual lead-related SAE to 1% at 5 years. The sample size for primary safety endpoint 1 was calculated based on the following assumptions:

### Assumptions for primary safety endpoint 1

- Study Design: nonrandomized registry
- Type I error (alpha): 0.05 (one-sided for noninferiority)
- Statistical power: 80%
- Noninferiority delta: 5%
- Estimated SAE-Free Rate at 5 years: 92.5% for Corox BP LV Leads

For primary safety endpoint 1, a total of 240 evaluable subjects implanted with Corox BP LV leads would be required to demonstrate the noninferiority within 5% of a SAE free-rate of 92.5%. Assuming a 50% loss to follow-up rate over 5 years of follow-up, a total of 480 (240/0.5) subjects would be required to evaluate primary safety endpoint 1. Enrollment will seek to achieve 240 evaluable subjects for each of the Corox BP LV leads.

### Assumptions for primary safety endpoint 2

- Estimated individual SAE rate at 5 years: 0.4%
- Allowable two-sided, upper 95% confidence bound: 1%

For primary safety endpoint 2, a total of 1000 subjects would be required to demonstrate a two-sided, upper 95% confidence bound of 1%, assuming an expected individual SAE rate of 0.4% (no more than 4 patients with an SAE out of 1000). Assuming a 50% loss to follow-up rate over 5 years (10% per year), a total of 2000 (1000/0.5) enrolled patients would be required for evaluation of primary safety endpoint 2.

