## 2. STUDY ENDPOINTS

### 2.1 PRIMARY ENDPOINT 1: SAFETY OF COROX BP LV LEADS PACING – OVERALL COMPLICATION-FREE RATE

The primary safety endpoint will be evaluated in the following testable hypothesis in a noninferiority format.

$H_0$ : The serious adverse event-free rate (SAEFR) for the Corox LV Leads at 5 years post-enrollment is inferior to 92.5%

$$\text{SAEFR} + \delta \leq 92.5\%$$

$H_a$ : The serious adverse event-free rate (SAEFR) for the Corox LV Leads at 5 year post-enrollment is not inferior to 92.5%

$$\text{SAEFR} + \delta > 92.5\%$$

Where, ( $\delta$ ) is the clinically significant difference for establishing noninferiority. A rejection of the null hypothesis would indicate that the serious adverse event-free rate is not inferior to 92.5% within ( $\delta$ ).

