## 5. DESCRIPTION OF STATISTICAL METHODS

### 5.1 PRIMARY ENDPOINT 1: SAFETY OF COROX BP LV LEADS PACING – OVERALL COMPLICATION-FREE RATE

Primary endpoint 1 will be evaluated by performing an exact, noninferiority test comparing a binomial proportion (overall serious adverse event free-rate at 5 years) to 92.5%, with a noninferiority delta of 5% (87.5%). A lower 95% confidence limit greater than 87.5% will be considered evidence of statistical significance. A p-value will also be reported. This endpoint will be evaluated using the subject population defined in section 3.2 Primary Endpoint Per-Protocol (PP) Analysis Population.

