### 5.2 PRIMARY ENDPOINT 2: SAFETY OF COROX BP LV LEADS PACING – INDIVIDUAL COMPLICATION RATES

Primary endpoint 2 will be evaluated based on the exact, two-sided 95% confidence interval for the observed, individual serious adverse event rates at 5 years. The upper bound of these 95% confidence intervals must be less than 1%. This endpoint will be evaluated using the subject population defined in section 3.2 Primary Endpoint Per-Protocol (PP) Analysis Population.

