## **5.6 ADHERENCE AND RETENTION ANALYSIS**

A 50% loss to follow-up over 5 years (10% per year) will be assumed.

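### Both primary endpoints are tested in a set that drops patients who leave early without an event, which overstates the 5-year SAE rate if exit is unrelated to event risk

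*SAP*

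**What the plan says.** The null hypothesis for endpoint 1 (SAP 2.1) is that "The serious adverse event-free rate (SAEFR) for the Corox LV Leads at 5 years post-enrollment is inferior to 92.5" percent. SAP 2.2 sets a 1% limit for each SAE type at the same time point.

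The analysis set in SAP 3.2 holds patients who "have experienced a protocol defined primary endpoint AE or have a follow-up visit or system revision date completed 5 years post-implant", with the 5-year window opening at day 1781. In that set, "Primary endpoint 1 will be evaluated by performing an exact, noninferiority test comparing a binomial proportion" (SAP 5.1), and "Primary endpoint 2 will be evaluated based on the exact, two-sided 95% confidence interval" (SAP 5.2). Protocol 2.7.2 restricts the hypothesis tests in the same way and imputes nothing.

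On attrition, SAP 5.6 states: "A 50% loss to follow-up over 5 years (10% per year) will be assumed". Protocol 2.6 calls this figure an upper limit: "a maximum loss to follow-up of 10% per year (50% over 5 years) was assumed". It covers death, explant, withdrawal and loss of contact. The sample-size step divides by the retained share: "a total of 480 (240/0.5) subjects would be required to evaluate primary safety endpoint 1".

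An all-enrolled analysis exists, but only for monitoring: "Kaplan-Meier actuarial survivor curves will be prepared at the reporting intervals for these safety outcomes" (Protocol 2.7.1, with the censoring rule in 2.7.2). SAP 5.3.5 adds Kaplan-Meier curves by lead model, but the only population it names is the set of per-protocol subsets in SAP 3.3.

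**The concern.** Inclusion depends on the outcome. A patient with an event in year 1 who leaves in year 2 is analysed; a patient who leaves in year 2 without an event is not. The result is events divided by events plus event-free completers, which is not the 5-year rate in the hypotheses. The registry exists to report that rate. If it is inflated, an acceptable lead can miss a primary endpoint, and the reported rate is wrong whether or not the test passes.

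**Working it through.** **The plan's own figures.** An exact one-sided 5% test of 87.5% with n = 240 passes with at most 21 events. Its attained alpha is 4.4%, and its power at a true 92.5% is 80.7%. The divisions 240/0.5 = 480 and 1000/0.5 = 2000 also reproduce. The division treats completers as an unbiased sample of those enrolled.

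**Formula.** Let F be the true 5-year event risk, f(t) the event density and G(t) the probability of still being in the registry at time t, with exit independent of events.

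- Analysed events: E = ∫ f(t)G(t)dt over 0–5 years.
- Event-free completers: C = (1 − F)G(5).
- Tested rate: E/(E + C).

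This exceeds F exactly when E/F > G(5). E/F is the average retention at the times events occur. Retention only falls, so E/F cannot be below G(5), and the two are equal only if every event falls at year 5.

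**Assumptions.** F = 7.5% and 0.4% come from SAP 1.1. Event timing is not in the documents, so Weibull shapes 1 (constant hazard) to 3 (steeply rising) are used. Exit is linear or exponential. Loss is 50% (SAP 5.6), 41% (10% a year compounded: 1 − 0.9^5 = 0.41) or 20% (illustrative).

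**One case by hand: constant hazard, linear exit, 50% loss.**

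- λ = −ln(0.925)/5 = 0.01559 per year.
- ∫ t f(t)dt = 0.075/0.01559 − 5 × 0.925 = 0.185.
- E = 0.075 − 0.1 × 0.185 = 0.0565.
- C = 0.925 × 0.5 = 0.4625.
- Rate = 0.0565/0.5190 = 10.9%.

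Of 2500 enrolled, that is about 141 events among 1297 analysed. At about that size the endpoint 1 rule allows at most 142 events, so the test is close to a coin toss. An unbiased 1250 at a true 7.5% would pass almost surely.

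**Full range, 2500 enrolled.** The exact pass rules are applied with the analysed number treated as random. The endpoint 1 limit is taken as one-sided, as in Protocol 2.7.

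| Loss | True 7.5% reads | Endpoint 1 power, shape 1 | Endpoint 1 power, shapes 2–3 | Endpoint 2 pass at true 0.4%, shapes 1–3 | Endpoint 2 if unbiased |
|---|---|---|---|---|---|
| 50% | 8.9–10.9% | 54–70% | 92–99% | 24–45% | 62% (n = 1250) |
| 41% | 8.5–9.9% | 94–97% | over 99% | 45–62% | 76% (n = 1476) |
| 20% | 7.9–8.4% | about 100% | about 100% | 80–85% | 89% (n = 2000) |

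Allowing for the day-1781 window moves the 50% range to 8.8–10.7%. Outside these shapes, still at 50% loss, front-loaded events (shape 0.5) inflate the rate by 55–59% and very late events (shape 6) by 10–13%.

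**Check of the 240/0.5 step only.** At 50% loss, 480 enrolled gives 16–51% power over shapes 1–3, not 80%. The registry plans 2500, so this is not its actual power.

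**False passes at 50% loss, 2500 enrolled.** Below 0.01% for endpoint 1 (true 12.5%) and at most 0.3% for endpoint 2 (true 1%).

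**Does a planned Kaplan-Meier curve rescue the estimate?** In simulation, the all-enrolled curve returned 7.5%. A curve restricted to the SAP 3.2 type of set returned events/n exactly, because nobody there is censored event-free before the window opens. Run on the per-protocol sets, the secondary endpoint 5 curves would therefore repeat the biased proportion for each lead.

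**The case against.** The strongest reply is that the error is conservative and rarely decisive. Endpoint 1 is materially hurt only near 50% loss, which Protocol 2.6 calls a maximum, and only with a roughly constant or front-loaded hazard. Protocol 2.2 expects 7.5% or less; even in that corner, power is 83–91% at a true 7.0% and 96–99% at 6.5%. Both documents call endpoint 2 non-powered, and part of its weakness is sample size, since an unbiased 1250 passes only 62% of the time. FDA also receives the all-enrolled trend curves, which are compared with the same 92.5% and 99% targets.

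All of this stands, and it limits the severity. It does not remove the error: the trend curves decide neither endpoint, and endpoint 2 is still clearly affected at 41% loss.

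A reader might infer two stronger things.

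- *That the rule could make an unsafe lead pass.* Under independent exit the opposite holds. If exit is linked to event risk, which is possible because exits include deaths and explants, the direction is unknown and the documents give no basis for asserting it.
- *That the protocol and SAP use different denominators*, because Protocol 2.7.2 speaks of an SAE without qualification and Protocol 7.6 mentions unrelated SAEs, which might readmit some early exits as event-free. That reading is strained. Section 2.7.2 is about the primary endpoints and their hypotheses, so it most naturally means the endpoint's own SAE. Section 7.6 is about relatedness adjudication. On the natural reading the documents agree, and both carry the bias.

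**Conclusion.** The rule is wrong as written and should be fixed. If exit is independent of lead-SAE risk, a true 7.5% is overstated by 19–45% in relative terms at 50% loss (8.9/7.5 to 10.9/7.5) and by 14–32% at 41%, for Weibull shapes 1–3. The direction follows from the formula under independent exit; the size depends on event timing and exit pattern, which the documents do not give. The cost is an inflated reported rate, a real loss of power for endpoint 1 in one corner of the range, and a lower chance of success for endpoint 2 at 41–50% loss. It is not evidence that the registry would wrongly declare the leads safe.

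**What to change.** In Protocol 2.7 and 2.7.2 and SAP 3.2, 5.1 and 5.2:

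- **Estimator.** Base the primary rates and tests on the 5-year Kaplan-Meier estimate in all enrolled patients, censored at exit. Keep the thresholds: a one-sided 95% lower bound above 87.5% for endpoint 1, and a two-sided 95% upper bound below 1% for endpoint 2.
- **Bound.** Pre-specify one. An example is Clopper-Pearson on the effective sample size n = S(1 − S)/Greenwood variance, where S is the Kaplan-Meier SAE-free estimate, with n(1 − S) events. With zero events, use the exact interval on the number at risk when the window opens; at least 368 are then needed, since 1 − 0.025^(1/368) = 0.997%.
- **Time origin.** The hypotheses count from enrollment, but follow-up ends 5 years after implant and entry is 7–180 days after implant. Use time from implant in both documents, with patients joining the risk set at enrollment (delayed entry). State how events between implant and enrollment are counted.
- **Competing death.** Report cumulative incidence alongside, because Protocol 2.2 defines the rate as a proportion of subjects. If Table 4's death range (6.2–18.9%) applied over 5 years with linear deaths, a 7.5% Kaplan-Meier risk would correspond to about 6.4–7.3% of subjects.
- **Supportive and secondary.** Keep the exact completer proportion as supportive. Run any secondary endpoint 5 Kaplan-Meier curve on all enrolled patients with that lead.

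In simulations without delayed entry (2500 enrolled, 50% loss), this bound passed endpoint 1 about 100% of the time at a true 7.5% and endpoint 2 73–84% of the time at a true 0.4%. Endpoint 2 passed 1.6–2.1% of the time at a true 1%. For endpoint 1 at a true 12.5%, the pass rate at 50% loss was 4.1–4.9%.

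The cost is wording and one added analysis; no new data are needed. The test becomes approximate rather than exact, and censoring is assumed non-informative. The change favours the device while outcome reports go out every six months, so its date and rationale must be documented relative to those reports.

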#### 3.3 SECONDARY ENDPOINT PER-PROTOCOL (PP) ANALYSIS POPULATIONS

The secondary endpoint per-protocol subjects are a subset of the primary endpoint PP population, who are separated by the originally implanted Corox LV lead models. Subjects with a Corox LV lead replacement resulting in a change in lead model (e.g. Corox OTW-S BP to Corox OTW-L BP) and experiencing an event after the replacement will be analyzed with the originally implanted lead.

##### 3.3.1 Corox OTW BP (Helical) PP Analysis Population

The Corox OTW BP (helical) PP subjects are originally implanted with a Corox OTW BP (helical) lead and have experienced a protocol defined primary endpoint AE or have a follow-up visit or system revision date completed 5 years post-implant (defined as a visit completed on or after 45 days prior to the 5 year post-implant date, 1781 days).

##### 3.3.2 Corox OTW-S BP (Screw) PP Analysis Population

The Corox OTW BP-S (screw) PP subjects are originally implanted with a Corox OTW BP-S (screw) lead and have experienced a protocol defined AE or have a follow-up visit or system revision date completed 5 years post-implant (defined as a visit completed on or after 45 days prior to the 5 year post-implant date, 1781 days).

##### 3.3.3 Corox OTW-L BP (Dual-Curve) PP Analysis Population

The Corox OTW BP-L (dual-curve) PP subjects are originally implanted with a Corox OTW BP-L (dual-curve) lead and have experienced a protocol defined primary endpoint AE or have a follow-up visit or

system revision date completed 5 years post-implant (defined as a visit completed on or after 45 days prior to the 5 year post-implant date, 1781 days).

## 4. POOLABILITY ANALYSIS

For both primary safety endpoints 1 and 2, pooling of data from the Corox OTW BP, Corox OTW-S BP, and Corox OTW-L BP LV leads will be justified as part of the final data analysis. The differences in outcomes for the Corox OTW BP, Corox OTW-S BP, and Corox OTW-L BP LV leads will be tested using an exact, Chi-square test. If the sample size is too small to use a Chi-square test, Fisher's Exact test will be used to evaluate the differences in outcomes instead. If no evidence is found of differences between the Corox OTW BP, Corox OTW-S BP, and Corox OTW-L BP LV leads ( $p > 0.05$ ), then the results will be considered poolable for purposes of testing the protocol hypotheses associated with the two primary endpoints. If evidence of differences is found for a given endpoint, then the hypotheses for that endpoint will additionally be tested separately for each LV lead.

## 5. DESCRIPTION OF STATISTICAL METHODS

### 5.1 PRIMARY ENDPOINT 1: SAFETY OF COROX BP LV LEADS PACING – OVERALL COMPLICATION-FREE RATE

Primary endpoint 1 will be evaluated by performing an exact, noninferiority test comparing a binomial proportion (overall serious adverse event free-rate at 5 years) to 92.5%, with a noninferiority delta of 5% (87.5%). A lower 95% confidence limit greater than 87.5% will be considered evidence of statistical significance. A p-value will also be reported. This endpoint will be evaluated using the subject population defined in section 3.2 Primary Endpoint Per-Protocol (PP) Analysis Population.

### 5.2 PRIMARY ENDPOINT 2: SAFETY OF COROX BP LV LEADS PACING – INDIVIDUAL COMPLICATION RATES

Primary endpoint 2 will be evaluated based on the exact, two-sided 95% confidence interval for the observed, individual serious adverse event rates at 5 years. The upper bound of these 95% confidence intervals must be less than 1%. This endpoint will be evaluated using the subject population defined in section 3.2 Primary Endpoint Per-Protocol (PP) Analysis Population.

### 5.3 SECONDARY ENDPOINTS

There are no formal hypothesis tests associated with the secondary endpoints.

#### 5.3.1 Secondary Endpoint 1

Secondary endpoint 1 examines the successful biventricular pacing in a BIOTRONIK CRT device at scheduled CELESTIAL registry follow-up visits. The mean, standard deviation, minimum, and maximum of the biventricular pacing percentage will be reported for each visit. This endpoint will be evaluated using the subject population defined in section 3.1 Intention-to-Treat (ITT) Analysis Population.

#### 5.3.2 Secondary Endpoint 2

Secondary endpoint 2 examines the rates of serious adverse events excluded from primary safety endpoint. The serious adverse event rates will be reported along with a Kaplan-Meier actuarial graph and case summary will be reported to assess this endpoint. The estimated freedom from adverse event at 5 years along with the standard error and 95% confidence intervals will also be reported. This endpoint will be evaluated using the subject population defined in section 3.1 Intention-to-Treat (ITT) Analysis Population.

#### 5.3.3 Secondary Endpoint 3

Secondary endpoint 3 examines the sensing, pacing threshold, and pacing impedance measurements for the Corox LV leads at scheduled CELESTIAL registry follow-up visits. The mean, standard deviation, median, minimum, and maximum of each measured values be reported for each visit. This endpoint will be evaluated using the subject population defined in section 3.1 Intention-to-Treat (ITT) Analysis Population.

#### 5.3.4 Secondary Endpoint 4

Secondary endpoint 4 examines the individual electrical parameters of the Corox OTW BP LV lead, the Corox OTW-S BP LV lead, and the Corox OTW-L BP LV lead. The electrical parameters presented will be the sensing, pacing threshold, and pacing impedance measurements for each lead model at scheduled CELESTIAL registry follow-up visits. The mean and standard deviation of each measured value will be

reported for each visit. This endpoint will be evaluated using the subject population defined in section 3.1 Intention-to-Treat (ITT) Analysis Population.

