7.10 Other Institutions and Physicians	29
8. RECORDS AND REPORTS	30
8.1 Investigator Records.....	30
8.2 Investigator Reports	30
8.3 Sponsor Records.....	31
8.4 Sponsor Reports.....	32
APPENDIX A: DEFINITION OF TERMS	33
APPENDIX B: TIMELINE	37

Table of Figures

Figure 1: Corox OTW Bipolar LV Leads	11
---	-----------

Table of Tables

Table 1: Implant Success Rate Comparison	7
Table 2: Corox BP LV Lead: Pacing Parameters	8
Table 3: Comparison of Freedom from Adverse Events in the Corox BP LV Lead to Other Published Study Results	9
Table 4: Adverse Event Exclusions	13
Table 5: Primary Safety Endpoints Sample Sizes	16

CELESTIAL POST-APPROVAL REGISTRY

PROTOCOL SIGNATURE PAGE

The signature below constitutes the receipt and review of the CELESTIAL protocol and any attachments, and provides the necessary assurances that this registry will be conducted according to all stipulations of the protocol, including all statements regarding confidentiality, and according to local legal and regulatory requirements and applicable U.S. federal regulations, ICH and GCP guidelines.

PRINCIPAL INVESTIGATOR:

Signed: _____ Date: _____
Name (please print)

Signature Date: _____

PROTOCOL SUMMARY

Title:	CELESTIAL Post-Approval Registry
Design:	This study is a long-term post approval registry designed to follow at least 2500 patients implanted with BIOTRONIK's Corox BP left ventricular lead. Each patient will be followed for 5 years.
Purpose:	The purpose of this post-approval registry is to confirm long-term safety and successful biventricular pacing for BIOTRONIK's Corox BP left ventricular (LV) pacing leads as used in conjunction with any BIOTRONIK CRT pulse generator (CRT pacemaker (CRT-P) or CRT defibrillator (CRT-D)). The evaluation of safety will be based on the analysis of Corox BP LV lead related adverse events. The CELESTIAL post-approval registry will provide data to permit characterization of any LV lead failures contributing to patients losing CRT. Additionally, acute and chronic LV lead parameters for pacing thresholds and impedance will be evaluated.
Patient Population:	Patients who require treatment for advanced heart failure through any CRT-P or CRT-D. Patient must be successfully implanted with a BIOTRONIK CRT system, including a Corox BP LV lead, from 7-180 days prior to enrollment.

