2. STUDY DESIGN

The CELESTIAL post-approval registry is a multi-center, prospective, non-randomized, 5 year data collection registry. The registry is designed to gather long term safety and reliability data on BIOTRONIK's Corox BP LV leads. All patients enrolled into the clinical study will have an implanted BIOTRONIK CRT system, including a Corox BP LV lead, and will be enrolled from 7-180 days after successful CRT implantation or system revision.

Patients will be followed for 5 years post-implant, and are meant to be seen according to each institution's standard of care, but not to exceed a follow up time frame of (1) every 6 months for CRT pacemakers (CRT-Ps) or (2) every 4 months for CRT defibrillators (CRT-Ds). At enrollment, information will be collected regarding patient medical history, demographics, and other secondary data or data of interest specifically pertaining to the implant and status of the LV lead. At each follow up, a determination will be made whether the system is providing appropriate biventricular pacing. Additionally, the electrical parameters of the left ventricular lead will be collected, and any LV lead related adverse event will be documented.

The primary safety endpoints are constructed to capture all LV lead-related serious adverse events (SAEs) that require additional invasive intervention to resolve. Individual analysis of each serious adverse event (SAE) will be conducted and reported throughout the study. The low probability of SAE mandates the registry study size of a minimum of 2000 patients.

A secondary effectiveness endpoint will utilize a responder analysis of the success/failure of the CRT generator implanted with the Corox BP LV lead to deliver long-term biventricular pacing through 5 years post-implant.

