2.7 DATA ANALYSIS

For both primary safety endpoints 1 and 2, pooling of data from the Corox OTW BP, Corox OTW-S BP, and Corox OTW-L BP LV leads will be justified as part of the final data analysis. The differences in outcomes for the Corox OTW BP, Corox OTW-S BP, and Corox OTW-L BP LV leads will be tested using an exact, Chi-square test. If no evidence is found of differences between the Corox OTW BP, Corox OTW-S BP, and Corox OTW-L BP LV leads ($p > 0.05$), then the results will be considered poolable for purposes of testing the protocol hypotheses associated with the two primary endpoints. If evidence of differences is found for a given endpoint, then the hypotheses for that endpoint will additionally be tested separately for each LV lead.

CELESTIAL REGISTRY PROTOCOL

Primary safety endpoint 1 will be evaluated by performing an exact, noninferiority test comparing a binomial proportion (overall SAE free-rate at 5 years) to 92.5%, with a noninferiority delta of 5%. Equivalently, the upper, one-sided 95% confidence bound for the absolute difference between the overall SAE free-rate and 92.5% must not exceed 5%.

The evaluation of primary safety endpoint 2 will be based on the exact, two-sided 95% confidence interval for the observed, individual SAE rates at 5 years. The upper bound of these 95% confidence intervals must be less than 1%.

The secondary endpoint of successful biventricular pacing will be summarized as a success rate at each of the scheduled CELESTIAL follow-up visits through 5 years post-enrollment, together with the associated exact, 95% confidence intervals.

The secondary endpoint of other SAEs at 5 years, which were excluded from the primary safety analyses (listed in Table 5), will also be summarized as SAE rates together with their associated exact, 95% confidence intervals.

The secondary endpoints of pacing threshold and impedance measurements for the Corox BP LV leads will be summarized at scheduled visits where they were evaluated, using standard measures, including means, standard deviations, medians, minimums, and maximums.

The secondary endpoint for overall incidence of serious adverse events that meet the primary endpoint 1 criteria will be evaluated separately for each Corox BP lead model using the criteria established for primary safety endpoint 1 and 2.

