3.2.5 Routine and Unscheduled Follow-Ups

Patients enrolled in the CELESTIAL post approval registry can be implanted with either a CRT Pacemaker (CRT-P) or a CRT Defibrillator (CRT-D). Follow-up schedules for these devices vary by practice, but typically occur every 3-4 months for a CRT-D and every 6 months for a CRT-P. Therefore patients will be seen for routine follow-up visits per their institutional standard of care, but not to exceed every 6 months. All scheduled follow up windows are ± 1 month.

Any time a patient is seen outside of a required follow-up window according to each site's pre-determined specific follow-up scheduling practice, that visit is considered an unscheduled follow-up. Each site Principal Investigator (PI) and Clinical Research Coordinator (CRC) will be trained to identify and schedule follow-ups to meet this expectation. Additionally, the EDC will provide assistance in identifying properly scheduled follow-ups according to this protocol by assisting in the selection of the proper electronic Case Report Form (eCRF).

The following are required at each follow-up visit:

- Interrogate programmed parameters
- Determine lead electrical parameters
- Evaluate device diagnostics and programmed parameters to ensure CRT is programmed "ON" and the device is correctly providing CRT therapy
- Record % of CRT pacing
- Determine if there are any cardiac-related Adverse Events. If there are, complete the Adverse Event eCRF
- Complete all appropriate eCRF's

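### SAP 5.3.1 summarises the pacing percentage only and drops the protocol's per-visit biventricular pacing success rate with exact 95% CI; neither document defines success

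*SAP*

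**What the plan says.** Protocol 2.7 (Data Analysis) treats the endpoint as binary. It states: "The secondary endpoint of successful biventricular pacing will be summarized as a success rate at each of the scheduled CELESTIAL follow-up visits", and continues "through 5 years post-enrollment, together with the associated exact, 95% confidence intervals".

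Protocol 2 (Study Design) takes the same view: "A secondary effectiveness endpoint will utilize a responder analysis of the success/failure of the CRT generator implanted with the Corox BP LV lead". That sentence runs to 5 years post-implant and does not mention individual visits. The per-visit commitment comes from 2.7, which counts from enrolment.

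SAP 5.3.1 keeps the endpoint's name but plans a summary of a continuous variable: "The mean, standard deviation, minimum, and maximum of the biventricular pacing percentage will be reported for each visit". SAP 3 describes secondary endpoints 1 to 4 as continuous. SAP 5.5 refers figures, tables and listings to a final report template, which is not among the documents supplied.

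On data collection, Protocol 2 says that at each follow-up "a determination will be made whether the system is providing appropriate biventricular pacing". Protocol 3.2.5 requires a check that CRT is on and that "the device is correctly providing CRT therapy", and separately has the item "Record % of CRT pacing".

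**The concern.** The protocol promises a proportion with an interval, and the SAP delivers four summary statistics of a different variable under the same name. The Purpose entry of the Protocol Summary says that the registry is to "confirm long-term safety and successful biventricular pacing", and Protocol 2 calls this the secondary effectiveness endpoint. A reader of the final report would want to know what fraction of patients were successfully paced at each visit. An analyst who follows SAP 5.3.1 would not produce that figure.

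The adverse-event analyses do not fill the gap. They cover lead-related causes of lost CRT, and under Protocol 7.6 some problems corrected by reprogramming alone are not reportable as adverse events.

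The definition is also open. The visit-level judgement, the device check and the recorded percentage could each define success, and neither document chooses. If the choice is made after the data are seen, the cut-off can be driven by the data.

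**Working it through.** The documents state no sample size, power or target for this endpoint, so there is no figure to reproduce. The check has two parts.

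**1. The texts side by side**

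| Item | Protocol | SAP |
|---|---|---|
| Type of endpoint | Success/failure (2; 2.7) | Continuous (3; 5.3.1) |
| Summary per visit | Success rate (2.7) | Mean, SD, minimum, maximum (5.3.1) |
| Interval | Exact 95% CI (2.7) | None |
| Definition of success | Not given | Not given |
| Reason for the change | Not applicable | None given |

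**2. Can the SAP's statistics recover the protocol's proportion?**

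Sample sizes come from Protocol 2.6 (2500 enrolled, at most 10% of enrolment lost per year, 50% over 5 years):

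- 1-year visit: 2500 × 0.9 = 2250
- 5-year visit: 2500 × 0.5 = 1250

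Everything else is assumed, because the documents give no values: whole-percent readings, minimum 0, maximum 100, the means and SDs below, and 90% purely as an example cut-off.

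Two data sets of 2250 patients show the problem and can be checked by hand:

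- **A:** 17 patients at 0, 1 at 32, 862 at 89 and 1370 at 100. The sum is 32 + 76,718 + 137,000 = 213,750, so the mean is 213,750/2250 = 95. The squared deviations from 95 total 17×9025 + 3969 + 862×36 + 1370×25 = 222,676, so SD = √(222,676/2249) = 9.95, or 10.0 to one decimal (9.9504 before rounding). The share at or above 90% is 1370/2250 = **60.9%**.
- **B:** 19 patients at 0, 888 at 90, 94 at 95 and 1249 at 100. The sum is 79,920 + 8,930 + 124,900 = 213,750, so the mean is again 95. The squared deviations total 19×9025 + 888×25 + 0 + 1249×25 = 224,900, so SD = √(224,900/2249) = 10.0. The share at or above 90% is 2231/2250 = **99.2%**.

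Both would print the same line in the SAP's table: mean 95, SD 10.0, minimum 0, maximum 100.

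An integer programme gives the full bounds. It fixes the mean, matches the SD to one decimal, requires at least one patient at 0 and one at 100, and minimises or maximises the count at or above 90:

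| Mean, SD | n = 2250 | n = 1250 |
|---|---|---|
| 95, 10.0 | 1370 to 2231 (60.9% to 99.2%) | 762 to 1239 (61.0% to 99.1%) |
| 97, 5.0 | 1695 to 2249 (75.3% to 99.96%) | 982 to 1249 (78.6% to 99.9%) |

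For contrast, the protocol's own analysis at an assumed 90% success rate gives these exact (Clopper-Pearson) 95% intervals:

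- 2025/2250: 88.7% to 91.2%
- 1125/1250: 88.2% to 91.6%

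The two sets of ranges measure different things. The first is what the SAP's summary leaves undetermined; the second is ordinary sampling error.

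**The case against.** The strongest reply has four parts.

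- **The SAP does not withdraw the success rate.** It lists four statistics, the protocol still stands, and the unseen report template may include the rate. This limits the claim to an omission from the supplied SAP text; it does not show that the rate will go unreported. But a table template is no substitute for a methods section that defines success and names the interval.
- **SAP 3 calls secondary endpoints 1 to 4 continuous, which could explain the change.** It is the only SAP text that bears on the point. It is offered there as the reason for using the intention-to-treat population, not for replacing a proportion with a mean, and it does not mention the protocol's plan.
- **The numerical ranges are extremes built on assumed inputs.** This is correct. They also assume that every retained patient has a reading at a common visit, although schedules differ by site and device. They show only that the proportion is not identifiable, which is all the argument needs.
- **The endpoint is secondary, untested and descriptive, and the percentage is collected, so a rate can be computed later.** This also stands, and it limits the weight of the point. What remains is that a later rate would rest on a definition chosen after the data were available.

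**Conclusion.** The concern holds. The current protocol and SAP texts disagree on how secondary endpoint 1 is summarised. Followed as written, the SAP does not give the proportion of patients with successful pacing at any visit, and its four statistics cannot be converted into one. Under the stated assumptions they leave that proportion anywhere between about 61% and 99% (mean 95, SD 10.0), or between about 75% and almost 100% (mean 97, SD 5.0, n = 2250). The mismatch itself rests on the text alone; only the illustration depends on the assumed mean, SD, extremes and cut-off. Alpha, power, sample size and both primary conclusions are untouched. This should be corrected before analysis, but it does not threaten the registry's main results.

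**What to change.** In SAP 5.3.1:

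1. Restore the proportion with successful biventricular pacing at each scheduled visit, with its exact 95% CI, and keep the pacing-percentage summary as supportive.
2. State before analysis which collected item defines success: the per-visit determination, if the eCRF stores it, or the recorded pacing percentage with a pre-specified cut-off.
3. State how patients with an abandoned LV lead or with CRT programmed off are counted in the numerator and denominator.

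If the sponsor prefers the continuous summary alone, the SAP should say that it departs from Protocol 2.7 and why.

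A separate, SAP-wide item can be settled in the same revision. Protocol 2.7.2 also plans a last-value-carried-forward estimate at 5 years for pacing success, thresholds, sensing and impedance, and the supplied SAP text does not mention it. The SAP should either include it as a sensitivity analysis or say why it is omitted. The assumed 50% attrition includes deaths and explants (Protocol 2.6), so carrying values past those exits could flatter the 5-year result.

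The cost is one SAP paragraph, one definition, one table and one sentence on carried-forward values. The pacing percentage is already required at every follow-up. The eCRF is not among the documents, so whether it stores the per-visit determination has to be checked.
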